 - v. *Explain Video Release: Last is the video release. If you agree, we may use your videos from assessments and app sessions for training purposes in the future to continue helping other moms in the program. This may include other professionals to help them understand how the program works and how mothers use the program. Please check the box whether you agree or do not agree to this and type in your name. Again, this is optional and completely up to you.*
 1. If mom agrees, the next page will ask for her address. Tell her to complete that info then submit the form. Confirm receipt.
 2. If mom does not agree, the form will submit and she is done.
- b. Phone service & apple ID
 - i. *Last, I will be sending you 2 pieces of information through Coach Talk on the app. One has the Gmail account and Apple ID information and passwords. We created the Gmail in order to create the Apple ID, so it is yours now. You can keep it and use it or you can go in and delete it. I will send the passwords for both account as well as the answers to the security questions for you to access your Apple account.*
 - ii. *The second information is about the phone and service. The phone will be paid for until [month] 16th (ex. if you are doing a post on March 26, the phone will be paid for until April 16).*
 1. If phone is unlocked (check with [name] prior to call): *The phone is unlocked and can be switched to any service. If you want to keep it on a Sprint personal account or move to Boost, please let us know as soon as*

possible – we can initiate that transfer through our account. If you move it to another service, they will change the sim card to that service. You will need the account pin number listed on the sheet, so have that handy when you take it to the provider you want to switch to. If you do not move it to a personal service, you can continue to use it on WiFi. I will send you all of this info immediately after this call and you will get a reminder about a week before the service shuts off.

2. If the phone is NOT unlocked (check with [name] prior to call):
Unfortunately, the phone is not unlocked and cannot be transferred to a different company at this time. If you want to transfer it to a personal Sprint account, we can initiate that. I will send the phone number for Sprint if you want to see how much their plans are. You can also continue using the phone on WiFi – all the apps will work and you can use a wifi calling app like Google Voice, Skype, or Text Now for calls and texts. I will send you all of this info immediately after this call and you will get a reminder about a week before the service shuts off.
- c. *What final questions do you have?*
- d. *We really appreciate you participating and hope you have enjoyed the program!* End call as you normally would end the program on a mom's final call.

Immediately After Post Assessment Call(s)

5. Send mom Account Information and Phone Information through Coach Talk
 - i. Account info
 1. Dropbox -> MomAndBabyNetNIHR01 -> Participant Data -> [open folder with mom's ID #] -> '[ID] account info' PDF
 2. Mom will need all account info for AppleID and Gmail + security questions and answers
 - ii. Phone service info
 1. Dropbox -> MomAndBabyNetNIHR01 -> Assessment -> Assessment Protocols & Forms -> Remote Post Assessments
 2. Document 'Your iPhone Form for User at End of Project – [locked or unlocked]' – can copy and paste to mom in Coach Talk
6. Save videos to Dropbox as follows (Dropbox -> MomAndBabyNetNIHR01 -> Participant Data -> [participant's folder])
 - a. Rename files the drag and drop into participant folder
 - i. [ID] POST free play instructions [date]
 - ii. [ID] POST free play [date]
 - iii. [ID] POST book instructions [date]
 - iv. [ID] POST book [date]
7. Complete documents and save documents to Dropbox (Dropbox -> MomAndBabyNetNIHR01 -> Participant Data -> [participant's folder])
 - a. ASRI

- i. Mark appropriate boxes, add report if necessary, and add signature (printed or digital)
 - ii. Email to [name] if consultation needed (if self harm endorsed)
 - iii. Save or scan/save as “[ID] POST ASRI [date]” (if consult needed, only save final version with all signatures)
- b. Data Checklist
 - i. Check off all appropriate boxes, initial, and date
 - ii. Save or scan/save as “[ID] POST Data Checklist [date]”

8. Update Access

- a. Update scheduled appointments form
 - i. Change ‘scheduled’ to ‘complete’
 - ii. If mom completed everything in one call, mark second day as ‘canceled’ and in notes write ‘call not needed – mom completed on first call’

9. Update Matriculation table

- a. Assessment tab: Mark post assessment completed (Y)
- b. Training tab: enter date of post assessment and length of time in program

10. Project coordinator will complete

- a. Matriculation table
 - i. Mark model release signed (Y or N)
 - ii. Enter follow up assessment dates
- b. Project calendar
 - i. Enter follow up dates
- c. Download survey PDFs and save to participant folder
- d. Update follow up contact info (email & phone)
 - i. Access
 - ii. Qualtrics

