 - a. *I will email you a copy of the project's consent form. This document will explain in detail the purpose of the Mom and Baby Net project, what you will be doing in the project, and how we will keep your information safe. We are taking necessary precautions to keep you, your family, and our staff healthy during the Coronavirus pandemic. The Pre-assessment and training visits will be conducted remotely using Zoom – an app that allows us to have a video call. I will later explain how Zoom works if you choose to participate.*
 - b. *The iPhone agreement form will also be emailed to you. This document covers expectations of loaning you the iPhone to complete the Mom and Baby Net project. Your phone service will be covered while you are participating in the program. We will monitor your progress on a month to month basis. If you are making progress and staying in communication with your coach, we will renew your service for the next month. If we lose contact with you, or you are not making progress in the program, your phone service may be discontinued; If we cannot reach you and your phone is not returned, it will be reported as lost or stolen.*
 - c. *I will also mail a copy of both of these forms to your home. Have you still been receiving mail and packages as usual during this time?*
 - d. *What questions do you have? [answer any questions]*
 - e. *The next step is to schedule a call to talk about the Consent and iPhone agreement forms after you receive them in the mail. You will do this call with your Coach, who will be with you for the rest of the program. She will go over both of these forms, answer any questions you have, and explain the next step which will be sending the iPhone and materials to you. Please think about a time where you will be able to talk for about 15 minutes and she will reach out tomorrow to schedule that call.*

3. Confirm email and mailing address

After Consent Scheduling Call

1. Assign participant ID and enter into Access
2. Notify coach ASAP to reach out to participant to schedule consent call.
3. Mail & email Consent and iPhone agreement
 - a. Note to add in email/envelope: We will review these documents on our next call. After all your questions are answered, you will sign them, take a picture of each signature page, and will text them to the project staff member who you speak with on that call.

Day Before Consent Call

1. Call or text mom to confirm she received the consent & iPhone agreement in the mail

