 1. *Do you have laptop or tablet that is on data and/or wifi?*

 - i. If yes: *Great – if you would like, you can use your laptop/tablet to do the surveys. You can connect to Zoom on the project iPhone.*
 - ii. If no: *That is fine – you will be able to use the project iPhone to complete everything.*
 2. *The videos need to be created away from other people so that the interaction will not be interrupted by other people in the home; The video will need to be created away from sources of noises that could be picked up on the camera's microphone (like a noisy kitchen, television, or street). Where do you think the best place will be in your home to make the video?*
 3. Ask questions to help mom determine when would be the best time to do the call to record videos and complete the surveys. Some moms may know exactly when a good time is while others may need to think through some of these questions to figure it out. The purpose of these is to prime mothers for a successful video capture call.

 - i. *We want to make sure that we schedule the call at a time when your baby has been recently fed, is not sleepy and is feeling well AND when your other children are busy doing something fun that they like to do.*
 - ii. If there are other children in the home: *Was there a time yesterday when your older children were busy doing something that they were having fun with? What was it?* If it was appropriate, find out the details so you can encourage it for the call. If it is not appropriate or feasible, then help her think of something that is (i.e. watching an appropriate movie/show, playing a game). *When did they do that? Where? How long?* If the mother identifies something realistic and doable, encourage her to do that and have her set the specific reminder on her phone to get the other kids set up doing that activity 15 minutes BEFORE your scheduled call.
8. After working through these questions, schedule 2 1-hour sessions on different days, as close together as schedules allow (e.g., Wednesday & Thursday or Wednesday & Friday) with the mom to complete the pre assessment procedures. They should be 4-5 days after you drop off box of materials at UPS.

 1. Ask the mother to schedule the appointment times in her phone and show you:

 - i. 15 min before Call 1: Activity for other children
 - ii. Time of Part I Call (videos & Part 2 Qs)
 - iii. 15 min before Call 2: Activity for other children
 - iv. Time of Part II Call (Part 1 Qs)

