9. Confirm shipping address (for UPS packages) or physical address (if dropping off materials)
10. iPhone Customization Form
 1. *The last information we need from you is to set up your iPhone before we send it. We will create an Apple ID for the phone and you will get the password for that once you finish the program. That means you will not be able to add apps once you get the phone. We have to control the space on the phone to make sure there is enough space for our app to run smoothly while you are in the program. I am texting you a link to an online form where you can choose up to 10 apps to have on the phone. We will add those when we set it up.*
 2. Text mom link to iPhone customization form: [link & add to preassessment links page]
11. Wrap up & signature reminder
 1. *Do you have any final questions? [answer questions]. We are excited to have you in the program and thank you for your patience. Remember to sign the consent form and iPhone agreement and send me a photo of every page as soon as we get off the phone and complete the iPhone customization form using the link. Once we have that, we will get the phone and materials ready to send to you.*

After Consent Call

1. In Access, add appointment(s) as 'scheduled' for pre assessment (enter both dates and times on separate lines)
2. In Matriculation Table, list scheduled pre assessment date
3. Let Assessment Coordinator know as soon as participant texts Consent and iPhone Agreement (all pages, not just signature page). Assessment Coordinator will set up iPhone.
4. Prior to iPhone set up, the Intervention Project Coordinator implements randomization procedures. Using a random number generator, mother-infant dyads were randomized, in a 1:1 allocation, to one of the two parallel interventions: Mom and Baby Net or Depression and Developmental Awareness. The Intervention Project Coordinator notifies the PI to review condition assignment and assigns case to intervention coach.
5. Drop off/mail materials (Assessment Coordinator)
 2. Prior to dropping off bag to participant or box to UPS, confirm that mom texted signature pages.
 3. Drop off sanitized iPhone w/ case + headphones + charger + tripod + program handbook (make sure Zoom instruction card is in inside pocket) + books + welcome letter
 4. When you receive email confirmation that box has been delivered, call or text mom to confirm that she received everything.

Day Before Pre-Assessment Call

1. Send mom a reminder via text or call

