 - a. Remind her of time for scheduled call
 - b. Remind her that the videos need to be created:
 - i. At time when your baby has been recently fed, is not sleepy and is feeling well
 - ii. Away from other people so that the interaction will not be interrupted by other people in the home;
 - iii. Away from sources of noises that could be picked up on the camera's microphone (like a noisy kitchen, television, or street)

- c. Remind her, if applicable, of the fun activity for her older children, which they are going to get set up before the call with you
- d. Confirm that she has all the project materials that were sent to her & that her phone will be charged to at least 50% for the call. She will want to have headphones to use for the surveys unless it is just her and the baby in the home.

Pre-Assessment Call: Videos & Questionnaires [Assigned Coach]

(Split into 2 calls, 1 hour each; schedule 2 days as close together as possible)

1. Prior to getting on call
 - a. Gather needed paperwork (or go to electronic versions on Dropbox -> MomAndBabyNetNIHR01 -> Assessment -> Assessment Protocols & Forms -> Remote Assessments
 - i. ASRI
 - ii. Data checklist
 - iii. PDFs of surveys
 - iv. If mom is using a laptop/tablet to complete the surveys, have an email prepped with the link to send her. Do not send the day before.
2. Start Zoom call and greet mom as you normally would.
3. Zoom & iPhone orientation
 - a. Make sure mom is familiar with Zoom and troubleshoot if she has any issues with audio, video, etc.
 - b. Ask mom if she's ever used an iPhone before.
 - i. If not, give her a brief tutorial (turning off and on; answering phone; sending texts; Safari browsing; opening and closing apps; taking screenshots). Reference handbook section that covers this.
 - ii. Show mom all of the contacts that you added to her phone and explain the method for entering them (e.g., DR Smith Pediatrician; MED Poison Control). Reference handbook section that covers this.
 - iii. Show mom how to add numbers to Favorites (coach has already been added to favorites).
4. Review what you will be doing for the assessment part of the project

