- b. For moms in PALS condition only: When you get to setting mood anchor page, have mom pause zoom by returning to home screen, and advancing until she reaches page shown on screen. You will talk to mom about setting mood anchors as she does it on her device; She will then follow along with audio for the next couple of pages as she practices rating her mood.

8. For moms in the PALS condition who using Zoom on a device other than project iPhone

- a. Have moms set phone she is using on Zoom on tripod, and have her go through the pages on her project phone, as coach screen shares. Mom will be able to see both coach and video as she follows along
- b. For mom in PALS condition only: ask mom to show you her page when setting mood anchors and rating mood
- c. Review pages via screen sharing as you normally do during training visit and answer questions mom has about different pages in section menu of app.

Before ending the call

1. Schedule your Session 1 Zoom call with mom and show her how to use the calendar not only for reminding her of weekly Zoom calls, but for doctor's appointments or anything else she needs to schedule.
 - a. Have her enter your scheduled Zoom call and use a reminder.

- b. It is suggested that when you add coach appointments to your calendar that you include a 'day before' reminder as well as a 15-minute reminder and send an Invite. It would be great if moms have a regular time that can be set up to 'Repeat Weekly', but if not, you could send week to week.
- 2. Ask if there are any updates to her alternate contact info (at least 3); Confirm best means of contact for mom

After App Training Call

- 1. Update Access
 - a. Update scheduled appointments form
 - i. Change 'scheduled' to 'complete'
 - b. If needed, update contact information
- 2. Update Matriculation table
 - a. Training tab: Mark training visit completed (Y)

<>REMOTE POST ASSESSMENT PROCEDURES<>

Schedule Post Assessment

- 1. Coach will schedule post-assessment with mom during session 14 (or last) Coach Call as usual
 - a. *Typically, we would do the last visit in the home, but due to the coronavirus we will complete post assessments using Zoom as we did for our coach calls. Just as we did at the pre-assessment, you'll complete some questionnaires and we will make 2 videos of you and your baby. To get ready for our Post-Assessment Zoom Call, I'd like to get a little information from you.*

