 - a. Ask the mother to schedule the appointment times in her phone and show you:
 - i. 15 min before Call 1: Activity for other children
 - ii. Time of Part I Call (video & Part 2 Qs)
 - iii. 15 min before Call 2: Activity for other children
 - iv. Time of Part II Call (Part 1 Qs)

Immediately After Scheduling Call

- 5. In Access, add appointment(s) as 'scheduled' for post assessment (enter both dates and times on separate lines)
- 6. In Matriculation Table, list today's date as 'mom ready for post' and list scheduled post date
- 7. Email [name] the following information
 - a. Mom's ID
 - b. Scheduled post date
 - c. If mom needs books, send address (or confirm address listed in Access)
- 8. [name] will send back phone info (locked or unlocked) and Sprint PIN # (this changes periodically)

Day Before Post Assessment

- 2. Send mom a reminder via text or Coach Talk
 - a. Remind her of time of call tomorrow
 - b. Remind her that the videos need to be created:
 - i. At time when your baby has been recently fed, is not sleepy and is feeling well
 - ii. Away from other people so that the interaction will not be interrupted by other people in the home;
 - iii. Away from sources of noises that could be picked up on the camera's microphone (like a noisy kitchen, television, or street)

- c. Remind her of the fun activity for their older children, which they are going to get set up before the call with you
- d. Confirm that she has ear buds as these will be required unless she is alone with her baby throughout the assessment;
- e. Confirm that she has received the books that were sent and/or has books available for post call

3. Make sure you have or have access to all necessary information

Post Assessment Call: Videos & Questionnaire (1.5 hours) [COACH]

(Breaks during the call will be provided and most will be split into 2 separate calls)

- 1. Prior to getting on call
 - a. Gather needed paperwork (or go to electronic versions on Dropbox -> MomAndBabyNetNIHR01 -> Assessment -> Assessment Protocols & Forms -> Remote Assessments)
 - i. ASRI
 - ii. Data checklist
 - iii. PDFs of surveys
 - iv. PDF of follow up form
 - v. Phone info
 - vi. Participant account info (in individual participant folder on Dropbox)
- 2. Start Zoom call and greet mom as you normally would.
- 3. Review what you will be doing

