 17. After 5:30 minutes, stop recording on Zoom, unmute yourself, and say *Ok, the second video is finished.*
- e. Reset Zoom
 - i. *Great job on the videos! Now we can continue to the surveys. So we don't run out of time, I am going to end this call and we are going to get right back on this same Zoom to continue.*
 - ii. End Zoom call then start again immediately.
 - iii. Ask mom if she needs to take care of any needs for the baby or if she is able to put the baby down or give to another adult so she can focus on the surveys.

5. Questionnaires
 - a. Post Assessment Questionnaire Part 1 (labeled as part 2 in Qualtrics: T2_part2)
 - i. *Now we will begin the questionnaires. They are split into two parts, so we don't have to complete both today. They are very similar to the questionnaires you completed at your very first home visit. Each part will take 30-40 minutes to*

complete. We can start Part 1 and see how far we get. If we need to, we can complete the rest of the survey on our next scheduled call.

- ii. I am now sending you a link to the first survey we will complete. Please let me know when you have received it and you can go ahead and click on it.*
- iii. Send link to T2_Part 2 survey to mom
 1. Link: (see links document)
 2. If mom is doing surveys on their phone, text survey link to mom's project phone
 3. If mom is using laptop, email survey link
 4. If mom is restarting a partially finished survey, see steps below to get link to that survey and start where she left off
- iv. Coach will have PDF of survey open to look at (printed or on computer). If mom needs to stop before reaching the end of this survey, make a note on the PDF of where she ended.
- v. Set up surveys
 1. If mom is using their project phone: *When you click on the link, we will stay on Zoom. Even though we won't be looking right at each other through video, I will walk you through everything.*
 2. If mom is using own laptop/table: *If you want to set your phone up somewhere during these surveys, we will not necessarily need to see each other, but I will be walking you through each section of the survey.*
- vi. Coach will instruct mom how to fill out the first page of info: ID #, mom initials, assessor name, date (mm/dd/yyyy)
- vii. Read instructions for each section
 1. Coach will read through introductory instructions and instructions for first section.

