 2. *Please stop and let me know each time you get to a picture, which indicates a new section. I will go over the instructions for the new section and answer any questions you have. If you have questions while you are completing the survey, please stop and ask. I will be on Zoom the entire time.*
 3. *Finally, you'll let me know when you reach the stop sign at the end of the survey. After the stop sign, you'll continue to the final questions.*
- viii. When mom reaches stop sign, tell her to continue to next page (shows embedded safety data – will have to check once survey is submitted)
- ix. Tell mom to continue to next page to the Services questions.
 1. *I will go through these last questions with you.*
 2. Go through the services questions with mom and give her time to answer each question.
- x. Have mom hit final 'submit' button to record answers. She will see a full copy of the entire survey.
 1. *Great job - you have finished the first survey! Please give me a few minutes to make sure everything submitted ok.*
- xi. Check survey in Qualtrics

1. Coach will log into Qualtrics bit.ly/qualtricsGSU
2. Look for T2_Part 2 survey
3. Click on 3 dots to the right of that survey and click 'Data & Analysis'
4. Look for mom's ID # and info for that survey to confirm submission; if not there yet, wait a minute and refresh

xii. Record embedded data on ASRI

1. Record total PHQ score ('score' column in Qualtrics) on page 1 of ASRI and check 'yes' or 'no' for elevated score
 - a. If yes – ask mom if she has recently discussed her mood with a doctor; did the doctor have any recommendations?; were there any recommendations discussed between coach and mom during the program you can revisit?
2. Check PHQ self harm item (phq #9 column in Qualtrics)
 - a. If response of 1, 2, or 3 – check box
 - b. Tell mom: *The only responses I can see are items related to your safety and I wanted to follow up on this item.*
 - c. Follow decision tree, as usual, to address potential safety concern with mom
 - d. Check appropriate box under 'Self Harm' after completing decision tree discussion

xiii. Continue or prepare to finish the next day

1. If mom seems focused with no distractions, give her the option to continue to the second part of the survey

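### In the remote procedures baseline follows randomisation, and the mother's own coach, who knows the arm, runs the post outcome call

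*Protocol*

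**What the plan says.** **Home pathway.** In protocol section II an assessor completes the questionnaires and videos, then books the training visit at which the phone is handed over. Section III places phone set-up in the preparation for that training visit. Randomisation is to precede phone set-up, so it falls after baseline.

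**Remote pathway, baseline.** In section VI, After Consent Call, item 4 is the random-number step: "The Intervention Project Coordinator notifies the PI to review condition assignment and assigns case to intervention coach". Item 5 ships the phone, handbook and books. The baseline calls are timed from that shipment: "They should be 4-5 days after you drop off box of materials at UPS". They are headed "Pre-Assessment Call: Videos & Questionnaires [Assigned Coach".

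**Remote pathway, coach assignment.** Before consent, the coordinator is told: "Notify coach ASAP to reach out to participant to schedule consent call". The mother hears that this coach will stay with her throughout, and the consent call itself is labelled as the assigned coach's. Item 4 nevertheless assigns the case to a coach at randomisation.

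**Remote pathway, post.** The call is headed "Post Assessment Call: Videos & Questionnaire (1.5 hours) [COACH". The coach takes questions during the surveys and sends and checks a Part 1 survey whose label carries the arm. After an elevated PHQ score the coach is also prompted to ask: "were there any recommendations discussed between coach and mom during the program you can revisit". The script tells mothers: "Typically, we would do the last visit in the home, but due to the coronavirus we will complete post assessments using Zoom". Of the questionnaires it says: "They are very similar to the questionnaires you completed at your very first home visit".

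**SAP.** Aim 2 is a pre-post by group repeated measures ANOVA with no term for mode or assessor. The Random Sampling/Attrition section takes a significant Group effect at baseline as evidence that randomisation did not equate the arms. The SAP is dated 09/18/2016.

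**The concern.** A baseline taken before allocation cannot be affected by it. Once allocation comes first, that guarantee is lost, whether or not anyone uses the knowledge. A baseline group difference then has two possible explanations: chance imbalance, or an influence of assignment on the measurement. The SAP's check treats it as a sign of failed randomisation only. A dyad lost between randomisation and the remote calls would also have no pre score, although the SAP means to analyse everyone recruited.

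At post, the mother reports mood, parenting and stress on a call run by the person who has just coached her through one of the two programs. The two call guides differ in content: one works through skills, successes and an action plan, and the other is shorter and built around milestones. A tendency to answer favourably could therefore differ by arm. A tendency common to both arms cancels. Only a net between-arm shift in change reaches the Aim 2 test.

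**Working it through.** **1. Order of steps**

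| Step | Home (sections II and III) | Remote (section VI) |
|---|---|---|
| 1 | Consent and baseline, same visit | Consent call |
| 2 | Randomisation, before phone set-up | Randomisation, before phone set-up |
| 3 | Phone set-up, training visit | Phone set-up, shipping |
| 4 | Program | Baseline calls, then App Training, then program |

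The rule (randomise before phone set-up) is the same in both columns. In the remote column the phone is needed for baseline, so the same rule puts randomisation ahead of it.

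**2. Who is shown to know the arm, and when**

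- Remote baseline: not shown for mother or coach. The T1 survey names carry no arm label, and nothing says that the handbook, login or phone contacts differ by arm.
- App Training: the coach knows, because some steps are for one condition only.
- Post: the coach knows, because the survey is chosen by condition.

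**3. Scale of the SAP's effect sizes.** Inputs from the SAP Power Analysis: N = 150, alpha .05, r = .21 or .68. For the group by time F test (1 and 148 df), noncentrality = 2N f²/(1 − r). At 80% power it must be 7.95.

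- r = .21: f = sqrt(7.95 × .79/300) = .145, so 2f = .289 (SAP: .29)
- r = .68: f = sqrt(7.95 × .32/300) = .092, so 2f = .184 (SAP: .18)

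The 95% figures reproduce the same way (.372 and .237, SAP .37 and .23). So the SAP's detectable d is 2f. The between-arm difference in change in raw SD units is 4f, or .58 and .37. A raw shift is halved to put it on the SAP's d scale.

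**4. Illustration of bias.** The shift and the affected share are assumptions. Affected means a coach-run remote post, whatever the baseline mode. Bias = shift × share. SE of the difference in change = sqrt(2(1 − r)) × sqrt(2/75), which is .205 at r = .21 and .131 at r = .68. The noncentrality of the t test is bias/SE, with 148 df and two-sided .05.

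| Share | Shift (SD) | Bias (SD) | Type I error, r = .21 | Type I error, r = .68 |
|---|---|---|---|---|
| 25% | .1 | .025 | 5.2% | 5.4% |
| 25% | .2 | .05 | 5.7% | 6.7% |
| 50% | .1 | .05 | 5.7% | 6.7% |
| 50% | .2 | .10 | 7.7% | 11.8% |

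On the d = 2f scale the 50% rows are .025 to .05. If the SAP's anticipated effects are on that scale, which it does not state, this is 12.5% to 25% of d = .2 (infant) and 5% to 10% of d = .5 (maternal).

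**5. What a check by mode could detect.** With share s affected, SE of group by time by mode = sqrt(2(1 − r)) × sqrt(2/(75s) + 2/(75(1 − s))). At s = .5 this is .411 (r = .21) and .261 (r = .68). Power for a .1 SD shift is 5.7% and 6.7%, and for .2 SD it is 7.7% and 11.8%. For 80% power the shift must be 1.16 or .74 SD. At s = .25 it must be 1.34 or .85 SD.

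**The case against.** - **Knowledge of the arm at remote baseline.** A reader might infer that remote baselines were taken by a coach and a mother who knew the arm. The documents do not support that (working, step 2). What stands is the avoidable loss of protection.
- **A clean comparator.** A reader might also infer that home assessments were masked and independent. Home assessors are not said to be masked or to be different people from the coaches, and the risk form has a joint assessor/coach signature line. They too sit with the mother, may read items aloud and answer questions. Answering questions is therefore not peculiar to the remote call. Being the mother's own program coach is what the remote text adds explicitly.
- **Mixed mode.** That some mothers had a home baseline and a remote post is suggested by the script's wording. No count or date is given, and the same script serves all mothers.
- **Safeguards.** Mothers enter their own answers, video instructions are scripted, and the coach stays silent during recording. The coach is not said to score outcomes, and the video coders are not described. The likely route is self-report, so the observational codes are less exposed.
- **Size and timing.** Shift and share are both assumed. The manual partly uses the past tense, so enrolment may be over and little may remain to change.

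These points limit the weight of the concern. They leave standing the order of steps and the coach's role at post.

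**Conclusion.** The concern holds in a limited form. Two facts are clear from the text: remote baseline follows randomisation, and the coach who delivered the program runs the remote post call knowing the arm. The second matters more. The first is a needless weakness that also blurs the SAP's baseline check. Separately, the text conflicts with itself on whether the coach is assigned before consent or at randomisation.

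The documents do not establish that bias occurred. Under the assumed range (a net shift of .1 to .2 SD in 25% to 50% of dyads, 75 per arm, r from .21 to .68) it would be .025 to .10 SD in raw change, with type I error between 5.2% and 11.8%. It is negligible if few dyads are affected. Mothers know their program by post, so bias in self-report can be reduced but not removed. This should be changed where it still can be, with medium confidence.

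**What to change.** **Protocol section VI, for dyads still to be assessed**

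1. Move the random-number step to after both T1 surveys and both videos are submitted, and before App Training. Send or activate any arm-specific material or account only then. Cost: possibly a second delivery or later account set-up, if the handbook or account differs by arm.
2. Have the remote T1 and T2 outcome calls run by existing staff other than the mother's own coach, for example coaches swapping cases. Leave all safety and elevated-PHQ follow-up steps as the protocol states them, and reconcile the text on who performs them. Cost: one hand-off per mother and small script edits. The documents give no staffing numbers, so extra hours cannot be checked.
3. Reconcile the consent-scheduling and consent-call text with After Consent Call item 4 on when the coach is assigned. Cost: wording only.

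**SAP, Aim 2**

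Record for each dyad the mode and assessor type at pre and at post, and whether baseline preceded randomisation. Report the group by time effect by these in a descriptive sensitivity table. State that the table has little power (about 6% to 12% for a .1 to .2 SD shift with half affected), is confounded with the pandemic period and cannot rule out bias. Cost: a few recorded variables and one table.

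If enrolment is complete, only the SAP step applies.
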